Exploratory Aim 2: Validate the BACtrack Skyn wrist-worn alcohol sensor device against the industry standard Alcohol Monitoring Systems (AMS) Scram ankle-worn alcohol sensor device, as well as alcohol diary self-monitoring. We will conduct sensitivity/specificity analysis as well as linear regression comparing estimated blood alcohol level (BAL) after adjustment for covariates that may impact transdermal alcohol concentration including gender, body mass index (BMI), skin temperature, and physical activity levels.

2. **Probable Duration of Project:** State the expected duration of the project, including all follow-up and data analysis activities.

It is expected that the study will take 3 years to conduct and analyze.

3. **Background:** Describe the background information that led to the plan for this project. Provide references to support the expectation of obtaining useful scientific data.

Alcohol use disorder (AUD) onset peaks during young adulthood (i.e., 18-25).⁽¹⁾ Compared to older adults, young adults report more frequent and heavier alcohol consumption that is linked to substantial negative consequences including risk of accidental injury, the primary cause of death among young adults.⁽²⁻⁴⁾ Current alcohol intervention strategies for young adults have modest effects⁽⁵⁻⁷⁾ and young adults rarely self-identify for specialized alcohol treatment.^(8, 9) Thus, more work is needed to identify effective alcohol interventions and novel treatment engagement strategies to reduce this substantial public health burden.

HIC # 2000021048

One novel approach is to target poor sleep, a common complaint among young adults who drink heavily^(10, 11) and an AUD risk factor in young adults.⁽¹²⁻¹⁴⁾ Sleep problems in young adults may be due to important developmental changes in sleep that begin with puberty and continue into young adulthood. During this developmental period, there is a need for more sleep⁽¹⁵⁾ and a preference for later bed and wake times,⁽¹⁶⁾ which often conflict with school/work demands and social/cultural obligations.⁽¹⁷⁾ To cope with these conflicts, adolescents and young adults may maintain shorter, more variable sleep schedules putting them at-risk for sleep problems, excessive daytime sleepiness, and other negative consequences.⁽¹⁷⁻¹⁹⁾

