[REDACTED]	[REDACTED]	[REDACTED]	[REDACTED]	[REDACTED]
[REDACTED]	[REDACTED]	[REDACTED]	[REDACTED]	[REDACTED]
[REDACTED]	[REDACTED]	habits	[REDACTED]	[REDACTED]

[figure not shown]
A randomization ratio of 2:1:1 (stratified by gender) will be used to assign participants to conditions. Specifically, we will enroll twice as many participants in A+SM+F condition compared to the other 2 conditions. The larger sample will allow us to better evaluate the types of sleep/alcohol data feedback that young adults find helpful and acceptable. There are three types of sleep data: (1) quantitative sleep characteristics from the sleep tracker and sleep diary (e.g., sleep duration, sleep efficiency, percent awake, bed/wake times), (2) self-report ratings of sleep quality and sleepiness/sleep-related impairment upon

waking; and [REDACTED]. In addition, there are two types of alcohol data: (1) estimated blood alcohol level from the alcohol tracker and (2) self-reported alcohol consumption from the sleep diaries. The research assistant will demonstrate how to wear the Respiromics Actiwatch Spectrum Plus, the AMS Scram blood alcohol tracker, the Skyn Sensor blood alcohol tracker, how to access the sleep and alcohol diaries, and arrange to pick up the Actiwatches, AMS and Skyn Sensor blood-alcohol trackers, and chargers at the end of each 7-day monitoring period. To encourage compliance, we will compensate participants for each day that they complete daily sleep dairies.

Treatment Phase (Weeks 1-2): For 2 weeks following randomization, participants in all 3 conditions will wear a Respiromics Actiwatch Spectrum Plus sleep tracker, an AMS Scram blood alcohol tracker, and a Skyn Sensor blood-alcohol tracker daily. Those assigned to the 2 conditions that involve sleep/alcohol diary self-monitoring (i.e., A+SM; A+SM+F) will complete daily mobile application-based sleep diaries during the 2 weeks following intake.

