Feasibility	Adherence (diaries, trackers, tips)		X	X	X
Acceptability	Treatment evaluation; exit interview				2

Assessments:***Eligibility, Laboratory, Medical Assessments:***

Socio-demographic information will be assessed with interviews and self-report forms that provide data on age, race, socioeconomic and marital status, and educational and occupational levels.

Diagnostic and Substance Use History will be assessed by [name], licensed clinical psychologists, using the Structured Clinical Interview for DSM-V⁽⁶¹⁾ (i.e., current and past substance use disorders, other current Axis I psychiatric diagnoses). An **Alcohol Use Disorders Identification Test**, a reliable, valid alcohol use screener, will be administered to confirm the inclusion criterion of at-risk drinking based on recommended AUDIT-C cut-off scores for young adults.⁽⁴⁸⁾

Height and Weight will be assessed using a Health O Meter Professional scale and stadiometer from which we will calculate BMI.

Physical Fitness will be self-reported using the International Fitness Scale,^[85] a standardized, validated, and reliable five-question survey with likert-type responses for participants to rate their own physical fitness. This will

HIC # 2000021048

be assessed as a potential moderator of the validity of the BACtrack Skyn device (see statistical analysis, exploratory aim 2)

Urine Drug Toxicology will be based on a JANT Pharmaceuticals urine test kit for opiates, cocaine, barbiturates, amphetamines, benzodiazepines, or phenylcyclidine. Positive tests are an exclusion criterion.

Breath Alcohol Concentrations for in-person visits will be determined using a hand-held breathalyzer unit - an Alcohol-Sensor III (Intoximeter Inc., St. Louis, MO). Participants need to test negative to provide consent at intake and need to test <.04% at subsequent in-person treatment and assessment visits.

Drinking Measures

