G. Describe the provisions for protection of participant privacy *Write here*

H. Describe the methods for the security of storage and sharing of materials *Write here*

6. **Subject Population:** Provide a detailed description of the types of human subjects who will be recruited into this study.

HIC # 2000021048

Participants will be up to 140 male and female volunteers (plus up to 5 pilot subjects), 18-25 years of age, who report ≥ 3 heavy drinking occasions within the last 2 weeks and report having concerns about their sleep.

Participants must meet inclusion/exclusion criteria as listed below. Based on the demographics of New Haven and the surrounding communities obtained from census data, we anticipate the following breakdown: White (not Hispanic) 70%, Black 17%, White (Hispanic) 10%, Asian/Asian Indian 3%.

7. Check off all classifications of subjects that will be specifically recruited for enrollment in the research project. Will subjects who may require additional safeguards or other considerations be enrolled in the study? If so, identify the population of subjects requiring special safeguards and provide a justification for their involvement.

 Children	 Healthy	 Fetal material, placenta, or dead fetus
 Non-English Speaking	 Prisoners	 Economically disadvantaged persons
 Decisionally Impaired	 Employees	 Pregnant women and/or fetuses
 Yale Students	 Females of childbearing potential	

NOTE: Is this research proposal designed to enroll children who are wards of the state as potential subjects?

Yes No

8. **Inclusion/Exclusion Criteria:** What are the criteria used to determine subject inclusion or exclusion?

Participants will be eligible if they:

- (1) 18-25 years of age;
- (2) report ≥ 3 heavy drinking occasions in the last 2 weeks (i.e., ≥ 5 drinks on 1 occasion for men; ≥ 4 for women);
- (3) report having concerns about their sleep;
- (4) willing/able to complete daily sleep diaries and wear sleep and alcohol trackers;
- (5) report Alcohol Use Disorders Identification Test – Consumption (AUDIT-C) scores indicative of risk of harm from drinking (i.e., ≥ 7 and ≥ 5 for men and women, respectively);⁽⁴⁸⁾
- (6) read and understand English;

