For Exploratory Aim 2, we will validate the BACtrack Skyn wrist-worn alcohol sensor device against the industry standard AMS Scram ankle-worn alcohol sensor device, as well as alcohol diary self-monitoring. We will conduct sensitivity/specificity analysis as well as linear regression comparing estimated blood alcohol level (BAL) after adjustment for covariates that may impact transdermal alcohol concentration including gender, body mass index (BMI), skin temperature, physical fitness, and physical activity levels.

SECTION II: RESEARCH INVOLVING DRUGS, BIOLOGICS, RADIOTRACERS, PLACEBOS AND DEVICES

If this section (or one of its parts, A or B) is not applicable, check off N/A and delete the rest of the section.

A. RADIOTRACERS N/A

If NO, an FDA issued IND is required for the investigational use unless RDRC assumes oversight.

2.

B. DRUGS/BIOLOGICS N/A

2.

B. DEVICES N/A

SECTION III: RECRUITMENT/CONSENT AND ASSENT PROCEDURES

1. Targeted Enrollment: Give the number of subjects:

- a. Targeted for enrollment at Yale for this protocol: 140 + 5 pilot subjects
- b. If this is a multi-site study, give the total number of subjects targeted across all sites: *Write here*

2. Indicate recruitment methods below. Attach copies of any recruitment materials that will be used.

 Flyers	 Internet/web postings	 Radio
 Posters	 Mass email solicitation	 Telephone
 Letter	 Departmental/Center website	 Television
 Medical record review*	 Departmental/Center research boards	 Newspaper
 Departmental/Center newsletters	 Web-based clinical trial registries	 Clinicaltrials.gov
 YCCI Recruitment database	 Social Media (Twitter/Facebook/Instagram):	
 Other:		

* Requests for medical records should be made through JDAT as described at
<http://medicine.yale.edu/ycci/oncore/availableservices/datarequests/datarequests.aspx>

3. Recruitment Procedures:

- a. Describe how potential subjects will be identified. *Write here*

HIC # 2000021048

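### Fitness is named as a potential moderator of Skyn validity, but Exploratory Aim 2 only adjusts for it, so the stated analysis cannot answer that question

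*Combined protocol and SAP*

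**What the plan says.** In Section I, item 4 (Assessments, Physical Fitness), self-rated fitness will "be assessed as a potential moderator of the validity of the BACtrack Skyn device (see statistical analysis, exploratory aim 2". The cross-reference leads to the Exploratory Aim 2 paragraph of item 13: "We will conduct sensitivity/specificity analysis as well as linear regression comparing estimated blood alcohol level (BAL) after adjustment for covariates". Fitness appears there once, in the adjustment list: "after adjustment for covariates that may impact transdermal alcohol concentration including gender, body mass index (BMI), skin temperature, physical fitness, and physical activity levels". No interaction, stratified accuracy or other moderation analysis follows. The statement of the same aim in item 1 lists "gender, body mass index (BMI), skin temperature, and physical activity levels", without fitness.

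On the data, item 4 (Treatment Phase) has all three conditions wearing "an AMS Scram blood alcohol tracker, and a Skyn Sensor blood-alcohol tracker daily" for two weeks, and Section VI, item 2 pays for 14 days of Skyn wear. Diaries are narrower: "Those assigned to the 2 conditions that involve sleep/alcohol diary self-monitoring (i.e., A+SM; A+SM+F) will complete daily mobile application-based sleep diaries". Allocation is unequal: "A randomization ratio of 2:1:1 (stratified by gender) will be used to assign participants to conditions". Entry requires at least three "heavy drinking occasions in the last 2 weeks" (item 8).

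Item 13 gives a mixed model for within-person correlation under the Primary Aim and carries it to Secondary Aim 1. The Exploratory Aim 2 paragraph does not refer to it.

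**The concern.** Moderation of validity means that the relation between Skyn and its reference, or Skyn's sensitivity and specificity, differs by fitness. Entering fitness as a covariate estimates something else: the average difference in level at a given reference reading. A reader who follows the cross-reference finds a fitness coefficient that could be reported as moderation when it is only a shift, or dismissed when agreement does vary.

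The second matter is smaller. Each person can supply up to 14 days of readings, and the paragraph names neither the unit of analysis nor a method for repeated observations. If person-days were analysed as independent, the stated precision of sensitivity, specificity and the person-level terms (gender, BMI, fitness) would generally be too high.

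**Working it through.** The plan gives no power, precision or ICC figure for Exploratory Aim 2, so there is nothing to reproduce. The inputs from the protocol are up to 140 participants (item 6), up to 14 sensor days (Section VI, item 2) and 2:1:1 allocation (item 4). ICCs, the split of days, slopes and complete wear are assumptions.

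**1. What the main effect estimates.** Let Skyn = a + b·Ref + c·Fit + d·(Ref × Fit). Moderation is d; a level shift is c. If the interaction is left out, and Ref has the same distribution at each fitness level, the fitness coefficient becomes c + d·mean(Ref). With mean(Ref) = 1:

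- slope difference only (c = 0, d = -0.40): 0 + (-0.40)(1) = -0.40
- shift only (c = -0.40, d = 0): -0.40 + 0 = -0.40

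The adjusted model returns the same number for both. The interaction separates them: -0.40 against 0.00. In 2,000 simulated trials (140 people, 14 days, exponential reading with mean 1, residual variance 1 with ICC 0.3, fitness split 50:50, clustered errors) the main effect was significant in 98% of runs in either case. This illustrates the algebra; it says nothing about the true effect of fitness.

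**2. People available for each reference.** AMS: up to 140. Diary: 140 × 3/4 = 105, because the advice-only arm keeps no diary.

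**3. If person-days were pooled as independent.** Design effect = 1 + (m - 1)·ICC. Coverage of a nominal 95% interval = 2Φ(1.96/√design effect) - 1. The 14 days are split, by assumption, into 5 drinking and 9 non-drinking days.

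| Quantity | m | Design effect at ICC 0.1 / 0.3 / 0.5 | Coverage |
|---|---|---|---|
| Sensitivity | 5 | 1.4 / 2.2 / 3.0 | 90 / 81 / 74% |
| Specificity | 9 | 1.8 / 3.4 / 5.0 | 86 / 71 / 62% |
| Person-level regression term | 14 | 2.3 / 4.9 / 7.5 | 80 / 62 / 53% |

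A beta-binomial simulation at ICC 0.3 with 140 people (20,000 runs) gave naive coverage of 80.7% (m = 5) and 71.0% (m = 9), against 94.6% and 93.8% with participant-clustered intervals.

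Half-widths at ICC 0.3 are 1.96·√(p(1-p)/(N·m)), then multiplied by √design effect:

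- Sensitivity 0.80, AMS: 1.96·√(0.16/700) = 3.0 points; × √2.2 = 4.4. Diary (N·m = 525): 3.4, then 5.1.
- Specificity 0.90, AMS: 1.96·√(0.09/1260) = 1.7 points; × √3.4 = 3.1. Diary (N·m = 945): 1.9, then 3.5.

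**4. If the interaction is added.** It needs clustering too. In 600 simulated trials per setting with no true moderation (random-intercept variance 0.1/0.3/0.5, random-slope variance 0.05/0.1/0.2), ordinary regression rejected at a nominal 5% in 14.5/20.7/26.7% of runs; participant-clustered errors rejected in 6.3/6.7/5.5%.

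For its precision, take a 50:50 fitness split, within-person reading variance 1 and within-person residual variance 0.7 (1 - ICC 0.3). The slope difference detectable with 80% power is 2.80·√((SD² + 0.7/13)·4/N), where SD is the between-person slope SD. For SD from 0.1 to 0.4 this gives about 0.12 to 0.22 with 140 people and 0.14 to 0.25 with 105.

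**The case against.** The strongest reply is that this is a wording mismatch in an exploratory aim. The fitness paragraph says only that fitness is a potential moderator, no hypothesis about it is stated, and item 8 uses the word moderator just as loosely for marijuana and caffeine use. Fitness does appear in the cross-referenced paragraph, and relabelling it a covariate in item 4 would restore consistency. Most of this is fair. It would be too strong to say that the protocol commits itself to fitness being a moderator. But a potential moderator still needs an analysis that could show moderation, and relabelling would drop the question rather than answer it.

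A reader might also infer that items 1 and 13 contradict each other because item 1 omits fitness. They do not: the item 1 list is introduced as a set of examples, so aligning it is only an edit.

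A reader might further infer that the investigators will treat sensor days as independent. The documents do not support this. They are silent on the unit; a person-level summary regression would raise no repeated-days problem; and the team handles within-person correlation where it specifies repeated measures. Redacted text beside the drinking-log and tracker descriptions in item 4 could define days or episodes, although the Exploratory Aim 2 paragraph is not redacted. What stands is that the mixed model for the Primary Aim tests condition effects and is not extended to device validation.

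**Conclusion.** The main point holds from the text and the form of the model. The fitness paragraph points to an analysis that estimates a level shift and cannot show whether Skyn-reference agreement varies with fitness. The figure of -0.40 rests on assumed slopes; the inability to separate the two cases does not.

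The repeated-days point is secondary and conditional. The coverage losses apply only if person-days are pooled without clustering, and at ICCs the documents do not give. Even then point estimates are little affected, and the plan sets no acceptance threshold for accuracy that a wider interval could overturn. That the two references cover different numbers of people is a feature of the design, not an error, but it should be visible in the report.

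Severity is minor. The effect is confined to Exploratory Aim 2.

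**What to change.** In the Exploratory Aim 2 paragraph of item 13:

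1. State which device is the outcome and which the predictor. Add an exploratory interaction of fitness with the predictor reading (reference-by-fitness if Skyn is the outcome), or report sensitivity and specificity by fitness level.
2. State the unit of analysis. Specificity needs units that include non-drinking time, such as person-days; drinking episodes contain no reference-negative units. Since every entrant is a recent heavy drinker, whole persons are not a practical unit for it either.
3. If person-days are used, give participant-clustered intervals for sensitivity and specificity (for example a cluster bootstrap). For the regression, use participant-clustered errors or a mixed model with a random intercept and a random slope for the reading.
4. Report the number of people and of days separately for the AMS and diary references.

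Add fitness to the item 1 list for alignment only.

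The cost is plan wording and a few lines of code, with no new data. The downside is wider intervals in most cases and an interaction that may be imprecise, so it should be presented as an estimate with its interval.
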